#### Pre-administration of allopurinol (or suitable alternative)

Patients thought to be at risk of tumor lysis syndrome should be well-hydrated and treated with allopurinol (300 mg p.o.) or suitable alternative treatment for 12-24 hours before prior to the first dose of therapy with rituximab.

#### Caution: Do not administer rituximab as an intravenous push or bolus

Rituximab will be administered intravenously in an out- or in-patient setting. Oral premedication (1000 mg of paracetamol and 50-100 mg diphenhydramine hydrochloride) needs to be administered 30-60 minutes prior to starting each infusion of rituximab. Prednisone/prednisolone as part of the chemotherapy protocol will be administered in the prescribed dose before the infusion of rituximab, preferably as oral medication. A peripheral or central intravenous (iv) line will be established. Before starting the infusion, there should be a

ready supply of epinephrine for subcutaneous injection and diphenhydramine hydrochloride for intravenous injection, and resuscitation equipment for the emergency handling of anaphylactic reactions.

The infusion will be started at an initial rate of 50 mg/hour for the first hour. During the rituximab infusion, the patient's vital signs (blood pressure, pulse, respiration and temperature) will be monitored every 15 minutes (4x) for one hour or until stable and then hourly until the infusion is discontinued. If no toxicity is seen during the first hour, the dose rate may be escalated gradually (by increments of 50 mg/hour at 30 minute intervals) to a maximum of 300 mg/hour. If the first dose of rituximab is well-tolerated, the starting flow rate for administration of the second and subsequent infusions will be 100 mg/hour and then increased gradually (by 100 mg/hour increments at 30 minute intervals) not to exceed 400 mg/hour. Patients may experience transient fever and rigors with infusion. If any of the effects below are noted, the antibody infusion should be temporarily discontinued, the patient should be observed, and when the symptoms improve, the infusion should be continued but at half the previous rate.

Dose Rate	Fever	Rigors/chills	Mucosal congestion Edema	Drop in Systolic Blood Pressure
Decrease to 1/2 If any of these Events seen:	> 38.5°C	Mild/Moderate	Mild/Moderate	> 30 mm Hg

Following the infusion the intravenous line should be kept open for medications, as needed. If there are no complications, the intravenous line may be discontinued after one hour of observation.

Dosage: 375 mg/m^2 body surface

body surface	total dose
1.4 m 	525.0 mg
1.5 m 	562.0 mg
1.6 m 	600.0 mg
1.7 m 	637.5 mg
1.8 m 	675.0 mg
1.9 m 	712.5 mg
2.0 m 	750.0 mg

Hours	1st application mg/h *)	mg-total	further applications mg/h *)	mg-total
0 – 1	50	50	100	100
1 – 1.5	100	100	150	175
1.5 – 2	150	175	200	275
2 – 2.5	200	275	250	400
2.5 – 3	250	400	300	550
3 – 3.5	300	550	350	725
3.5 – 4	300	700	400	925
4 – 4.5	300	850		

\*) With a concentration of 1 mg/ml the values of mg/h are equal to ml/h

Suggested Rituximab Rapid infusion

If no adverse events occurred during first Rituximab infusion, with adequate premedication, II-III and IV Rituximab infusion will be performed as follows:

rituximab 375 mg/m 	First dose of 100 mg in saline solution 100 ml
	Second dose (to total dose) mg in saline solution 250 ml

time	ml/h
0-60	100
61-180	125

## ATTACHMENT 5

### Methotrexate schedule (> 500 MG and ≤ 3000 MG)

Day	Date	Time	Treatment	Nurse Signature
0	.../.../....	16:00 – 24:00	1000 ml Gluc / NaCl 2:1	
		20:00	2 cp Hydrochlorothiazide® 250 mg p.os.	
1	.../.../....	24:00 – 08:00	100 ml Gluc / NaCl 2:1	
			500 ml NaHCO3 1,4%	
		06:00	2 cp Hydrochlorothiazide® 250 mg p.os.	
		08:00 – 12:00	1000 ml Gluc NaCl 2:1	
		08:00 – 14:00	500 ml NaHCO3 1,4%	
		11:30 – 11:45	20 mg Metoclopramide in 100 ml NaCl 0,9% i.v.	
		Attention! Before Methotrexate infusion:		
		1. Diuresis has to be at least 1500 ml in the last 12 hrs and 500 ml in the last 4 hrs		
		2. pH must be 8 in two assessments		
		12:00	2 cp Hydrochlorothiazide® 250 mg p.os.	
2	.../.../....	12:00 – 14:00	.... mg Methotrexate in 500 ml NaCl 0,9%	
		14:00 – 22:00	1000 ml Gluc / NaCl 2:1	
		14:00 – 02:00	500 ml NaHCO3 1,4 %	
		.....	.....	
		18:00	2 cp Hydrochlorothiazide® 250 mg p.os.	
		22:00 – 06:00	1000 ml Gluc / NaCl 2:1	
		24:00	2 cp Hydrochlorothiazide® 250 mg p.os.	
		02:00 – 14:00	500 ml NaHCO3 1,4%	
		.....	.....	
		06:00	2 cp Hydrochlorothiazide® 250 mg p.os.	
3	.../.../....	06:00-14:00	1000 ml Gluc / NaCl 2:1	
		12:00	30 mg Calciumfolinate® i.v. bolus	
			2 cp Hydrochlorothiazide® 250 mg p.os.	
		14:00 – 22:00	1000 ml Gluc NaCl 2:1	
		14:00 – 02:00	500 ml NaHCO3 1,4%	
		.....	.....	
		18:00	1 cp 15 mg Calciumfolinate® p.os.	
			2 cp Hydrochlorothiazide® 250 mg p.os.	
		22:00 – 06:00	1000 ml Gluc / NaCl 2:1	
		24:00	1 cp 15 mg Calciumfolinate® p.os. . 2 cp Hydrochlorothiazide® 250 mg p.os.	
		02:00 – 14:00	500 ml NaHCO3 1,4%	
		06:00	1 cp 15 mg Calciumfolinate® p.os.	
			2 cp Hydrochlorothiazide® 250 mg p.os.	
		06:00 – 14:00	1000 ml Gluc / NaCl 2:1	
			1 cp 15 mg Calciumfolinate® p.os.	
		12:00	2 cp Hydrochlorothiazide® 250 mg p.os. then stop if MTX level is normal.	
		14:00 - .....	Upon clinical judgement: 1000 ml Glucose 5% (according to MTX levels post-48 hours)	
		14:00 - .....	Upon clinical judgement: 500 ml NaHCO3 1,4% (according to MTX levels post-48 hours)	
		.....	.....	
		18:00	1 cp 15 mg Calciumfolinate® p.os.	

Day	Date	Time	Treatment	Nurse Signature
3 (cont.)	.../.../.... (continued)	24:00	1 cp 15 mg Calciumfolinate® p.os.	
4	.../.../....		15 mg Calciumfolinate® p.os. must be administered every 6 hours up to 72 hours after MTX infusion start time.	

Hydric balance and wight: D1-3: every 12 hours (06:00 + 18:00)

After MTX infusion urinary pH must be > 8:

- if pH = 8, must be assessed every 6 hours
- if pH < 8, must be assessed each urine sample

Never administer Lasix during urine alkalinisation time.

For 6 hours after MTX diuresis must be > 1000ml. If under this value upon clinical judgement enhance hydric intake or diuresis. 24 hours diuresis must be at least 3000 ml.

MTX levels will be assessed 24 and 48 hours after the MTX start infusion time.

## ATTACHMENT 6

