##### INTERMEDIATE-DOSE MTX

Methotrexate 1.5 g/m^2

It will be administrated diluted in 500 ml of normal saline solution (NaCl 0.9%). A urine flow  $\geq$  125 ml/hr has to be recorded in the 12 hrs before the MTX administration.

For MTX handling and administration see Attachment 5.

Intermediate-dose Methotrexate courses will be repeated every 14 days for 2 cycles.

All patients will undergo interim restaging procedures after the 3rd course (and before the 4th) of R-CHOP. Clinical response will be re-assessed at the end of planned treatment, one-two month after the completion of the whole therapy, including radiotherapy. Additional imaging studies during the treatment phase will be done only if clinically indicated.

Patients with progressive disease at any time will be withdrawn from the study.

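### Attachment 5 prints 100 ml for the overnight Gluc/NaCl bag before methotrexate where the other eight timed bags are 1000 ml: probably a dropped zero, to be checked against the source page

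*Combined protocol and SAP*

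**What the plan says.** Section 6.1.1 gives the intermediate-dose methotrexate rule and refers sites onward: "For MTX handling and administration see Attachment 5". Attachment 5 is an hour-by-hour order sheet with a column for the nurse's signature.

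The sheet has nine timed Gluc/NaCl 2:1 entries. The one for 24:00-08:00, ahead of the infusion, is "100 ml Gluc / NaCl 2:1". Six of the others are "1000 ml Gluc / NaCl 2:1", and the remaining two give the same 1000 ml without the slash. Directly beneath the queried entry is a 500 ml bicarbonate row with no time of its own.

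Two rules govern urine output before the drug is given. Section 6.1.1 sets a minimum flow: "125 ml/hr has to be recorded in the 12 hrs before the MTX administration". Attachment 5 says: "Diuresis has to be at least 1500 ml in the last 12 hrs and 500 ml in the last 4 hrs". The sheet also requires a urine pH check before the infusion and a fluid balance at 06:00 and 18:00. After the infusion it sets a minimum urine volume and adds: "If under this value upon clinical judgement enhance hydric intake or diuresis".

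**The concern.** Eight of nine like entries agree, and the odd one differs by exactly a factor of ten. It fills 8 of the 12 hours over which the sheet demands high urine output, and both neighbouring entries before methotrexate are 1000 ml. A planned near-stop of this fluid there would run against the purpose of the sheet, and no text gives a reason for it.

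Because the sheet is meant to be carried out and signed line by line, a nurse could follow the printed volume literally. Section 4.2 admits patients up to age 80 with creatinine clearance from 45 ml/min, so hydration before methotrexate matters in this population. What is at stake is the fluid given overnight and possibly the timing of the dose.

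**Working it through.** **Inputs, all from Attachment 5 unless stated.** Gluc/NaCl entries as tabulated below; the untimed 500 ml bicarbonate row beneath the queried entry; 500 ml bicarbonate at 08:00-14:00; a 100 ml metoclopramide bag at 11:30-11:45; methotrexate at 12:00-14:00; minimum urine flow of 125 ml/h over 12 hours (section 6.1.1).

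**Step 1: rate of each bag = volume / hours.**

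| Entry | Volume | Hours | Rate |
|---|---|---|---|
| 16:00-24:00, day before | 1000 ml | 8 | 125 ml/h |
| 24:00-08:00 (queried) | 100 ml | 8 | 12.5 ml/h |
| 08:00-12:00 | 1000 ml | 4 | 250 ml/h |
| 14:00-22:00, 22:00-06:00 and 06:00-14:00, each listed twice after methotrexate | 1000 ml each | 8 each | 125 ml/h each |

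Seven entries run at 125 ml/h, one at 250 ml/h and one at 12.5 ml/h. Putting 1000 ml in the queried slot gives 1000 / 8 = 125 ml/h, the rate of every other 8-hour bag.

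**Step 2: all scheduled IV fluid in 24:00-08:00, with the untimed bicarbonate placed there.**

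- As printed: 100 + 500 = 600 ml, or 600 / 8 = 75 ml/h.
- If corrected: 1000 + 500 = 1500 ml, or 1500 / 8 = 187.5 ml/h.

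**Step 3: scheduled IV fluid in the 12 hours before methotrexate (00:00-12:00).** The 08:00-14:00 bicarbonate is taken to run evenly, so 4 of its 6 hours count: 500 × 4/6 = 333 ml. Oral fluid is not counted.

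- As printed: 100 + 500 + 1000 + 333 + 100 = 2033 ml.
- If corrected: 1000 + 500 + 1000 + 333 + 100 = 2933 ml.
- Difference: 900 ml, and 900 / 2933 = 31%.

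If the untimed bicarbonate falls outside this window, 500 ml comes off both totals: 1533 ml against 2433 ml, and 900 / 2433 = 37%.

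**Step 4: comparison with the urine requirement.** Section 6.1.1 gives 125 × 12 = 1500 ml, which matches the 12-hour figure in Attachment 5. Printed intake is 2033 / 1500 = 1.36 times that figure, and corrected intake is 2933 / 1500 = 1.96 times. Without the untimed bicarbonate, printed intake is 1533 ml, still just above 1500 ml.

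**Step 5: the last 4 hours.** The queried bag ends at 08:00, so this window is unaffected: 1000 + 333 + 100 = 1433 ml of IV fluid, against a requirement of 500 ml of urine.

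**The case against.** The strongest objection is that this may not be an error in the plan at all. It is one digit in a machine-read table that is visibly damaged: the bicarbonate row has lost its time, and the day labels are displaced. If the source page reads 1000 ml, there is nothing to correct. That stands, and it is why checking the page comes first. It is also true that six of the seven 8-hour comparators come after methotrexate and that no other text states a volume for this slot, so 1000 ml is inferred from the pattern.

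A reader might take the 12.5 ml/h to mean that overnight hydration falls tenfold. The documents do not support that. The figure describes one bag. With the bicarbonate row counted, the slot carries 75 ml/h, which is 40% below the 125 ml/h of the slot before it ((125 - 75) / 125) and 60% below the corrected 187.5 ml/h (900 / 1500).

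A reader might also infer that the urine requirement cannot be met on the printed order. Scheduled intake exceeds 1500 ml in both cases worked above. It falls below, to 100 + 1000 + 100 = 1200 ml, only if the untimed bicarbonate lies outside the window and the 08:00-14:00 bicarbonate also runs wholly after 12:00. Those are two unlikely readings taken together.

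The opposite inference, that the safeguards are certain to catch the shortfall, is not supported either. The requirement measures urine, not intake, and the diuretic tablets at 20:00 and 06:00 raise output without replacing fluid. A patient could pass on the printed order. One who fails would have the dose held, as the sheet intends.

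**Conclusion.** The point holds as a probable dropped zero, at low severity and with medium confidence. If the printed figure is what sites have, the order gives 900 ml less IV fluid in the 12 hours before methotrexate: about 2033 ml against 2933 ml (31% less), or 1533 ml against 2433 ml (37% less) without the untimed bicarbonate.

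These totals rest on four assumptions: methotrexate starts at 12:00 on Day 1 (the 12:00-14:00 row gives the hour, and the day is inferred from the sequence of rows); the untimed bicarbonate belongs to 24:00-08:00, except in the alternative shown; the 08:00-14:00 bicarbonate runs evenly; and oral fluid is ignored.

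The consequence is weaker overnight pre-hydration and possibly a delayed dose. A reader might go on to infer unsafe methotrexate exposure. The documents do not show it: the urine and pH conditions come before the drug, creatinine clearance is checked before each course (section 9.1.5), and urine volume and methotrexate levels are followed afterwards. Nor is there any demonstrated effect on an endpoint, the sample size or the analysis.

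**What to change.** Compare the 24:00-08:00 entry with the source page. If that page reads 1000 ml, no change to the volume is needed. If it reads 100 ml, obtain clinical confirmation, correct it to 1000 ml, print the time of the 500 ml bicarbonate row beneath it, and reissue the order sheet to sites. If clinicians confirm that 100 ml is intended, add a short note saying so.

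The cost is a page check and, if needed, one corrected figure, one added time and a reissue. Design, sample size and analysis are untouched.

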## **2. OBJECTIVES**

### **2.1. Primary objective**

To demonstrate safety and feasibility of the R-CHOP regimen in combination with intrathecal liposomal cytarabine and systemic intermediate-dose methotrexate followed by loco-regional radiotherapy in untreated patient with stage I and II Primary Testicular Lymphoma

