## 6.2. Dose modification and delay

Dose modifications may be made according to any observed toxicity during the previous cycle, as outlined below. Toxicities are to be assessed according to the National Cancer Institute Common Toxicity Criteria for Adverse Events (NCI CTCAE)

version 3.0, 12/12/2003, National Institute of Health (NIH) <http://ctep.cancer.gov/reporting/ctc.html>

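### Attachment 5 does not link a non-normal 48-hour methotrexate level to a repeat level or to folinate beyond the fixed 72 hours

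*Combined protocol and SAP*

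**What the plan says.** Section 6.1.1 gives methotrexate 1.5 g/m² in the consolidation phase and sends the reader to Attachment 5 for handling. On the schedule, "Intermediate-dose Methotrexate courses will be repeated every 14 days for 2 cycles".

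Attachment 5 is a timed order sheet with a column for the nurse's signature. On rescue and monitoring it says:

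- **Folinate.** A 30 mg intravenous bolus is followed by 15 mg tablets. The day 4 line states that folinate "must be administered every 6 hours up to 72 hours after MTX infusion start time". No level is attached to that endpoint.
- **Levels.** "MTX levels will be assessed 24 and 48 hours after the MTX start infusion time". No other level is scheduled.
- **Diuretic.** The hydrochlorothiazide entry at 48 hours adds "then stop if MTX level is normal".
- **Fluids after 48 hours.** Glucose and bicarbonate are listed with open end times under "Upon clinical judgement". The glucose line reads "1000 ml Glucose 5% (according to MTX levels post-48 hours", and the bicarbonate line carries the same condition.
- **Urine and fluid checks.** The sheet sets minimum diuresis before and after the infusion, urinary pH targets with a testing frequency, and a fluid balance and weight check every 12 hours on days 1 to 3.

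The sheet schedules no serum creatinine.

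**The concern.** A sheet that says what to do when the 48-hour level is normal accepts that it may not be. For that second case it covers the diuretic and, at discretion, the fluids. It is silent on folinate, which is the rescue drug, and on whether to measure the level again. Staff who follow the printed lines exactly reach 72 hours, where mandated rescue ends, without a scheduled level to show whether methotrexate has cleared.

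Two features of the trial make this worth settling in writing. First, the primary objective is "To demonstrate safety and feasibility of the R-CHOP regimen in combination with intrathecal liposomal cytarabine and systemic intermediate-dose methotrexate", so the safety of the methotrexate courses is part of what the trial sets out to show. Second, entry is open up to age 80 and down to a creatinine clearance of 45 ml/min (Section 4.2). The protocol also treats kidney function as relevant to these courses: creatinine clearance is on the pre-course list for consolidation (Section 9.1.5) but not on the list for R-CHOP (Section 9.1.3).

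The trial is multicentre. With no numeric value for normal and no rule after 72 hours, centres may handle the same level differently.

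**Working it through.** No sample-size or power figure is involved. The check is clock arithmetic, followed by a comparison of what each part of the protocol says about a non-normal 48-hour level.

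**1. Clock.** Take the start of the methotrexate infusion, 12:00 on the sheet, as 0 h. The day labels in the available text are displaced, so the clock times are used.

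- Folinate 30 mg: 24 h.
- Folinate 15 mg, listed individually: 30, 36, 42, 48, 54 and 60 h.
- Folinate 15 mg under the day 4 line: 66 and 72 h.
- Total: 30 + 8 × 15 = 150 mg, or 135 mg if the 72 h dose is read as excluded.
- Last scheduled level: 48 h.
- Last scheduled level to end of mandated folinate: 72 − 48 = 24 h. Folinate is given throughout those 24 hours.
- Levels scheduled after 48 h: 0.

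**2. What the 48-hour level changes on the sheet.**

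| Item | Level normal at 48 h | Level not normal at 48 h |
|---|---|---|
| Hydrochlorothiazide | Stop | Stop condition not met |
| Glucose and bicarbonate | Clinical judgement | Clinical judgement |
| Folinate | Continue to 72 h | Continue to 72 h; nothing further stated |
| Repeat methotrexate level | None scheduled | None scheduled |
| Serum creatinine | None scheduled | None scheduled |

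The stop condition cannot be read as covering folinate. It sits in the 12:00 diuretic entry, and folinate tablets follow without condition at 18:00, at 24:00 and on day 4.

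**3. Whether another section supplies the rule.**

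- Section 6.2 opens with "Dose modifications may be made according to any observed toxicity during the previous cycle, as outlined below". What follows covers CHOP and rituximab only.
- Section 8 allows any supportive treatment a patient needs, other than anti-cancer treatment. That permits longer folinate but does not direct it.
- Section 9.1.1 requires adverse-event monitoring but sets no level or rescue rule.
- Section 9.1.5 requires creatinine and creatinine clearance before each course, not after it.
- Section 10.2 lets the investigator stop further treatment on safety grounds. It does not address rescue for a dose already given.
- The Attachment 9 table is broken in the available text, so its biochemistry marks cannot be assigned to days with confidence. No interval is derived from it.

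None of these sections supplies the missing instruction.

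**The case against.** **The 72 hours is a floor, not a stop order.** The line states what every patient treated under the sheet must receive. A reader might infer that the protocol orders folinate to end at 72 hours even when methotrexate has not cleared. The documents do not support that: nothing forbids further doses, and Section 8 permits them. What ends at 72 hours is mandated rescue. This part of the objection stands.

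**The sheet already responds to a non-normal level.** The diuretic stop depends on the level, and glucose and bicarbonate are guided by it at the clinician's discretion. The reference to levels post-48 hours, with an open end time, may presuppose further measurements. This stands in part. None is scheduled, and the phrase is attached to the fluids, not to folinate.

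**The patient is not unmonitored.** A reader might infer that nobody watches renal function around the dose. In fact the sheet requires:

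- diuresis and urinary pH conditions before the infusion;
- more than 1000 ml of urine in the 6 hours after methotrexate, with a corrective step if it falls short;
- at least 3000 ml of urine in 24 hours;
- urinary pH testing every 6 hours, or on every sample when pH is below 8;
- regular fluid balance and weight.

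Section 4.3 also excludes a history of clinically relevant renal insufficiency. These safeguards are real and narrow the concern. None of them triggers a repeat level or further folinate.

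**Much is properly left to clinicians.** The sheet relies openly on clinical judgement, and how far to do so is partly a matter of preference. Against that, the sheet gives explicit if-then rules for urinary pH and for low diuresis, so a conditional rule for folinate would fit its style.

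**Conclusion.** The point holds as a narrow omission. It is not a contradiction, and no endpoint definition or analysis depends on it. Attachment 5 sets mandatory folinate to a fixed 72 hours whatever the level, schedules levels only at 24 and 48 hours, and ties a non-normal 48-hour level to neither folinate nor a repeat level.

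**Size.** Mandated rescue ends 24 hours after the last scheduled level, with no later level scheduled. With 35 patients and two courses each, the sheet would govern at most 35 × 2 = 70 courses. How many would have a non-normal 48-hour level is not given, and no estimate is made. A reader might infer that the omission would cause toxicity, but the documents do not show the size of any harm. Nor does the wait until the next required creatinine measure the gap: Section 9.1.5 only places that test before each course, without fixing the day, and does not tie it to rescue.

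**Assumptions.** The dotted rows in the available text are taken as blank order lines without printed instructions. Times are counted from the 12:00 start printed on the sheet.

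This is a cheap improvement to patient safety.

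**What to change.** Amend Attachment 5 in three places.

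1. State that 72 hours is the minimum duration of folinate.
2. Add the line: *If the 48-hour level is not normal, repeat the level with serum creatinine at 72 hours and at set intervals, and continue folinate until the level is normal.*
3. State the numeric value meant by normal, which would also make the existing diuretic instruction definite.

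The numeric value and the repeat interval are for the sponsor's clinicians to set.

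The cost is two or three lines on the sheet, plus extra blood tests and possibly a longer stay in courses where the 48-hour level is not normal. Treatment and testing are unchanged in courses with a normal 48-hour level, because the existing folinate to 72 hours is kept.

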### Creatinine clearance calculation

Creatinine clearance for men and women will be calculated according to the Cockcroft-Gault formula as follows:

$$\text{In men: } \frac{[(140 - \text{age}) \times \text{weight(kg)}]}{[72 \times \text{creatinine(mg/dL)}]}$$

$$\text{In women: } \frac{[(140 - \text{age}) \times \text{weight(kg)}]}{[72 \times \text{creatinine(mg/dL)}]} \times 0.85$$

Note:

Age (in years), weight (in kg), serum-creatinine (in mg/dL)

72 (normalized to 72 kg body weight and a body surface of 1.72 m^2)

## ATTACHMENT 7

